### 10.4.1 Definitions

In the context of missing data sensitivity analyses for the primary efficacy analysis we define, using the terms described in [Table 10-2](#),

---

 Text added as per modification 5 in integrated SAP, Version 4.1.

- a subject with unobserved rivaroxaban/aspirin follow-up time, as a rivaroxaban/aspirin follow-up non-completer for whom no unrefuted primary efficacy outcome event was documented and who is alive at the time of censoring,
- a subject’s observed rivaroxaban/aspirin follow-up time, as the time used in the primary efficacy outcome analysis (time under risk),
- a subject’s unobserved rivaroxaban/aspirin follow-up time, as the time from censoring to the global rivaroxaban/aspirin outcomes cut-off date for subjects with unobserved rivaroxaban/aspirin follow-up time and zero for subjects with no unobserved rivaroxaban/aspirin follow-up time.

With regard to the extent of “missing data”, we define

- the fraction of subjects with unobserved rivaroxaban/aspirin follow-up time, as the number of subjects with unobserved rivaroxaban/aspirin follow-up time divided by the number of subjects in the ITT population
- the fraction of missing rivaroxaban/aspirin follow-up subject-years, as the sum of the subjects’ unobserved rivaroxaban/aspirin follow-up time divided by the sum of the subjects’ observed and unobserved rivaroxaban/aspirin follow-up time

These definitions rely on the division of the ITT study population into rivaroxaban/aspirin follow-up completers and rivaroxaban/aspirin follow-up non-completers, see [Table 10-2](#).

**Table 10-2. Definition of sensitivity analysis subject characteristics**

Subgroups	Definition
Rivaroxaban/aspirin follow-up non-completer	Subjects alive for whom 
 
• the last contact date during rivaroxaban/aspirin portion of the study is before the global rivaroxaban/aspirin outcomes cut-off date.
 

Rivaroxaban/aspirin follow-up completer	Subjects for whom 
 
• the last contact date during rivaroxaban/aspirin portion of the study is at or after the global rivaroxaban/aspirin outcomes cut-off date
 
• subject died
 

Rivaroxaban/aspirin study treatment non-completer	Subjects 
 
• who are rivaroxaban/aspirin follow-up non-completers and/or
 
• whose date of last rivaroxaban/rivaroxaban placebo or date of last aspirin/aspirin placebo study treatment is before the global rivaroxaban/aspirin outcomes cut-off date or before the subject’s death date (whatever comes first)
 

Rivaroxaban/aspirin study treatment completer	Subjects 
 
• who are rivaroxaban/aspirin follow-up completers and
 
• whose date of last rivaroxaban/rivaroxaban placebo and date of last aspirin/aspirin placebo study treatment is at or after the global rivaroxaban/aspirin outcomes cut-off date or identical to the death date
 

Note: the follow-up definitions from [Table 10-2](#) do not depend on

- premature discontinuation of study medication,

- the experience of an unrefuted primary efficacy outcome (rivaroxaban/aspirin follow-up non-completers may have experienced an unrefuted primary efficacy outcome event before premature discontinuation of their rivaroxaban/aspirin follow-up. However, only rivaroxaban/aspirin follow-up non-completers for whom no unrefuted primary efficacy outcome event is documented might impact the primary analysis due to missing outcome information.) and/or
- the reasons for being a rivaroxaban/aspirin follow-up non-completer, for example “complete withdrawal of informed consent”, “lost to follow-up”, or “other”.

Subjects who died are considered rivaroxaban/aspirin follow-up completers and having no missing outcome information, because subjects who experienced a terminal event cannot be followed-up.

#### **10.4.2 Descriptive comparison of baseline characteristics and post-randomization events**

Subjects who prematurely discontinue rivaroxaban/aspirin follow-up (rivaroxaban/aspirin follow-up non-completers) may differ systematically from subjects who complete rivaroxaban/aspirin follow-up. This concern is particularly important if these differences depend on and are different for the study treatment groups.

Therefore descriptive comparisons of key baseline characteristics and post-randomization events preceding end of the rivaroxaban/aspirin follow-up will be conducted. The comparison can provide indirect evidence that the degree of differential nonignorable censoring might be limited.

The analyses will be done for the following subgroups:

- rivaroxaban/aspirin follow-up completers who completed study treatment with rivaroxaban and aspirin
- rivaroxaban/aspirin follow-up completers who prematurely discontinued study treatment with rivaroxaban or aspirin
- rivaroxaban/aspirin follow-up non-completers.

For each subgroup the proportion of subjects with certain baseline characteristics and selected post-randomization events (or means) will be presented by treatment group.

To provide indirect evidence for ignorable censoring, those descriptive comparison will also be conducted for the groups of

- rivaroxaban/aspirin follow-up non-completers for which no unrefuted primary efficacy outcome event was documented
- rivaroxaban/aspirin follow-up completers and non-completers for which an unrefuted primary efficacy outcome event was documented.

In Section 10.4.3, a sensitivity analysis to investigate the potential impact of missing data on the primary efficacy analysis is described. To provide indirect evidence that the selection of the study cohort of subjects from whom information about the unobserved event process is borrowed is reasonable, the descriptive comparison will also include the group of

- subjects who prematurely discontinued any anti-thrombotic study treatment and who are not in the group mentioned above: rivaroxaban/aspirin follow-up non-completers for which no unrefuted primary efficacy outcome event was documented.

Baseline characteristics considered in these analyses are

- Coronary artery disease
- Peripheral artery disease
- CABG surgery (planned within 4-7 days) before randomization
- History of any prior CABG
- Region (North America, Western Europe and AUS/ISR/ZAF, Eastern Europe, Asia Pacific, and South America)
- History of a prior heart failure
- History of (non-lacunar ischemic) stroke
- History of prior MI
- History of prior asymptomatic carotid artery stenosis  $\geq 50\%$ / revascularization
- Age ( $<65$ , 65 years or older)
- Baseline renal function: estimated glomerular filtration rate (eGFR) ( $<60$  mL/min,  $\geq 60$  mL/min)
- Baseline diabetes
- Smoking at baseline

Selected post-randomization events are

- occurrence of an unrefuted major bleeding event
- occurrence of at least one serious adverse event/event of special interest (SAE/ESI)
- hospitalization
- premature discontinuation of blinded rivaroxaban treatment
- premature discontinuation of blinded aspirin treatment.

For the occurrence of major bleedings and SAEs/ESI only events occurring (start date) during the 90 days preceding the unrefuted primary efficacy outcome event or the censoring date relevant for primary analysis will be considered. For subjects observed for less than 90 days after randomization, only the time after randomization will be considered.

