## 10.4 Sensitivity analyses to address the potential impact of missing data

For the purpose of the sensitivity analyses described in this Appendix, missing data as related to the primary analysis is unobserved follow-up time up until the global rivaroxaban/aspirin outcomes cut-off date. Unobserved follow-up time may occur due to subjects who are non-compliant with study follow-up, for example due to loss of follow-up or premature complete withdrawal of informed consent. Subjects censored administratively at the “global rivaroxaban/aspirin outcomes cut-off date” or censored at time of non-CV death are not contributing missing follow-up time.

In the primary analysis, missing data due to rivaroxaban/aspirin follow-up non-completion before experiencing an unrefuted primary efficacy outcome event is addressed by assuming that such censoring is noninformative/ignorable in a sense like the (missing at random) MAR assumption. That is to say the assumption of its independence from the possibly unobserved time-to-event applies: the possibly unknown true time to the event for a subject is the same regardless of whether or not it is actually observed (or whether censoring occurs or not prior to it) (Zhao, 2014).

Subjects who prematurely discontinue rivaroxaban/aspirin follow-up (rivaroxaban/aspirin follow-up non-completers) may differ systematically from subjects who complete rivaroxaban/aspirin follow-up, thus introducing the possibility of non-ignorable censoring.

Non-ignorable censoring is differential if it leads to bias in the comparison of treatment groups, that is, if the differences in the hazard due to nonignorable censoring in the treatment groups do not “cancel out.” (Little et al., 2016).

The sensitivity analyses described in this Appendix to the SAP address the potential impact of missing data on the primary efficacy outcome and follow the elements described by Little et. al. (2016), involving two steps:

1. A descriptive comparison of key baseline characteristics and post-randomization events preceding the end of rivaroxaban/aspirin follow-up to assess whether subjects with missing data differ systematically from subjects who complete the rivaroxaban/aspirin follow-up.
2. A pattern mixture model using multiple imputation techniques to investigate the potential impact of missing data on the primary efficacy analysis if non-ignorable censoring is assumed to be differential.

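### In the completer versus non-completer comparison (SAP Appendix 10.4.2), hospitalization lacks the 90-day window given to bleeding and SAE/ESI, so its row depends on length of follow-up and counts the primary event's own admission

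*SAP*

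**What the plan says.** Appendix 10.4 makes a descriptive comparison the first of two steps on missing data. Its purpose is "to assess whether subjects with missing data differ systematically from subjects who complete the rivaroxaban/aspirin follow-up".

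Appendix 10.4.2 gives the details:

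- **Measure.** "For each subgroup the proportion of subjects with certain baseline characteristics and selected post-randomization events (or means) will be presented by treatment group". These are proportions, not rates per person-time.
- **Groups.** These include completers on and off study treatment, non-completers, non-completers without a primary event, and "rivaroxaban/aspirin follow-up completers and non-completers for which an unrefuted primary efficacy outcome event was documented".
- **Post-randomization items.** There are five: unrefuted major bleeding, SAE/ESI, hospitalization, and premature discontinuation of blinded rivaroxaban and of blinded aspirin.
- **Window.** "For the occurrence of major bleedings and SAEs/ESI only events occurring (start date) during the 90 days preceding". The look-back closes at one of two dates, whichever applies to the subject: that of the unrefuted primary event, or that at which the primary analysis censors the subject. A further rule covers short observation: "For subjects observed for less than 90 days after randomization, only the time after randomization will be considered". Both rules belong to bleeding and SAE/ESI; hospitalization is not named.
- **General bound.** The only limit that reaches hospitalization is that the comparison concerns "post-randomization events preceding end of the rivaroxaban/aspirin follow-up will be conducted".

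Table 10-2 defines non-completers as alive with a last contact before the global cut-off of 06 February 2017. Completers have a last contact on or after that date, or died. Hospitalization in this trial is for any cause: the tertiary objective in Section 2 says so, and Section 6.2.3.1 lists it separately from cardiovascular hospitalization.

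**The concern.** A cumulative proportion grows with time at risk. Two of the rows are put on a common 90-day basis, and the hospitalization row beside them is not. Two consequences follow.

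First, non-completers are observed for less time than they would have been had they stayed to the cut-off, while surviving completers reach it. At the same underlying risk, fewer non-completers will show a hospitalization.

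Second, everyone in the primary-event group has had an MI, a stroke or a CV death. Without a window ending before that event, its own admission and any later one are counted. Event-free non-completers have no counterpart to these admissions.

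The table is offered as indirect evidence on ignorable censoring and on the choice of the cohort whose hazards are borrowed for imputation. A reader who compares the hospitalization row across subgroups may take a difference in follow-up for a difference in risk, or may miss a real one.

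**Working it through.** The SAP gives no figure to reproduce here. The check is an illustration with a constant first-hospitalization rate *r* and follow-up *t*, using P(at least one) = 1 − exp(−*r* × *t*). The documents give neither hospitalization rates nor follow-up by subgroup, so these are assumptions: *r* from 0.05 to 0.20 per year, and non-completers vs completers followed for 0.5 vs 2, 1 vs 2 and 1 vs 3 years. The window is 90/365.25 = 0.2464 years.

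**1. Equal risk, unequal follow-up**

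| Rate/year | 0.5 vs 2 years | 1 vs 2 years | 1 vs 3 years | 90-day window, both groups |
|---|---|---|---|---|
| 0.05 | 2.5% vs 9.5% (3.85) | 4.9% vs 9.5% (1.95) | 4.9% vs 13.9% (2.86) | 1.2% |
| 0.10 | 4.9% vs 18.1% (3.72) | 9.5% vs 18.1% (1.90) | 9.5% vs 25.9% (2.72) | 2.4% |
| 0.20 | 9.5% vs 33.0% (3.46) | 18.1% vs 33.0% (1.82) | 18.1% vs 45.1% (2.49) | 4.8% |

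In brackets: completers divided by non-completers. With no true difference the ratio runs from 1.8 to 3.9, and with the window it is 1.0 throughout. The widest gap, 0.5 vs 3 years, would give more: at 0.05 per year, 13.9% / 2.5% is about 5.6 (1 − exp(−0.15) over 1 − exp(−0.025)).

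**2. Non-completers at truly higher risk**

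The proportion increases with *r* × *t*. With a hazard ratio HR for non-completers, the row points the wrong way when HR × t(non-completers) < t(completers), that is, when HR is below the follow-up ratio. At 0.15 per year in completers followed for 2 years, 1 − exp(−0.30) = 25.9%. Non-completers then show:

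- HR 1.5, 1 year: 1 − exp(−0.225) = 20.1%. Reversed (follow-up ratio 2).
- HR 2, 1 year: 1 − exp(−0.30) = 25.9%. Masked.
- HR 1.5, 1.5 years: 1 − exp(−0.3375) = 28.6%. Right direction (follow-up ratio 1.33), but 28.6/25.9 = 1.1 instead of 1.5.
- HR 1.5, 90-day window: 1 − exp(−0.0554) = 5.4% against 1 − exp(−0.0370) = 3.6% in completers. Ratio 1.5.

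**3. The primary event's own admission**

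Assume 1 year of observation in each group, a background rate of 0.10 per year (9.5%), and probability *q* that the primary event leads to admission. The event group shows 1 − (1 − *q*)(1 − 0.095):

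- *q* = 0.5: 55%
- *q* = 0.9: 91%

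Event-free non-completers show 9.5%. With a 90-day window ending before the event, both show 2.4%. In the plain completer versus non-completer comparison this effect is smaller. At the planning rate of about 2.9% per year in SAP Section 7, 1 − exp(−0.058) = 5.6% of subjects followed for 2 years have a primary event.

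**The case against.** The best reply has four parts.

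- **The SAP is silent.** It nowhere says that hospitalization is counted over the whole study, and Section 1 leaves programming instructions to a separate output specification that is not at hand. This stands as a limit: the unrestricted count is inferred from a window that names only two items. But someone following Appendix 10.4.2 as written has no other bound to apply than the end of follow-up.
- **No rule is broken.** Only bleeding and SAE/ESI are required to precede the primary event. This is correct. The point is that the chosen measure is unsuitable, not that the SAP contradicts itself.
- **The layout is by treatment group.** The appendix is most concerned with differences that vary by arm, and an arm-to-arm contrast within one subgroup is much less exposed to a follow-up gap between subgroups. This stands and narrows the point to reading across subgroups, which the completer versus non-completer and ignorable-censoring comparisons invite.
- **Little depends on it.** Hospitalization is one of 18 listed items (13 baseline, 5 post-randomization), with no test or threshold. Major bleeding is the only post-randomization covariate in the imputation model. This stands too.

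Three stronger readings are tempting, and the documents do not support them. A reader might infer that the table makes dropouts look healthier even when they are sicker. That depends on the hazard ratio being below the follow-up ratio, as the 1.5 vs 2 year case shows, and it concerns one row only. A reader might infer that subjects with a primary event will almost all appear hospitalized. The outcome includes CV death, which need not involve admission, and the 55% to 91% rests on assumed admission probabilities. A reader might infer that the missing-data analysis is compromised. Hospitalization does not enter it.

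The follow-up gap is itself a tendency: completers include everyone who died, some of them early.

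**Conclusion.** The point holds in limited form. As written, the hospitalization row is a crude proportion compared across subgroups whose follow-up differs through their definition, and in the primary-event group it includes admissions for or after the event. It tends to understate risk in non-completers. The spurious ratio of 1.8 to 3.9 rests on the assumed rates and the three assumed follow-up pairs, with a constant hazard; the trial's own figures could lie outside that range. Masking or reversal of a true excess is conditional, not general.

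What is weakened is the use of this row as indirect evidence on ignorable censoring and on the borrowing cohort. The primary analysis, the imputation model and the tipping point are unaffected. This is a minor, worthwhile correction.

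**What to change.** Add hospitalization to the existing date rule in Appendix 10.4.2. Count a subject as hospitalized only if an admission date falls within the 90 days before the unrefuted primary event or the primary-analysis censoring date, and not on that date itself, so that admission for the primary event does not count. Apply the same short-observation rule. The filter must search all of a subject's admissions, not only the first.

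Alternatively, report hospitalization per person-time up to the event or censoring date, excluding the primary event's own admission.

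The cost is one sentence and a date filter. Time to first hospitalization is already a tertiary variable in Section 6.2.3.1, so admission dates are needed in any case. There are two downsides:

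- Cells will hold fewer hospitalizations.
- Section 4.5.3 allows censoring at a contact that gave survival status only. For those subjects the last 90 days may hold no hospitalization information, so a windowed count could also understate non-completers. Flag these subjects and show their number by subgroup and arm.

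The two discontinuation items also lack a window. Discontinuation defines several of the groups, so a footnote stating their time basis would suffice.

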### 10.4.3 Sensitivity analysis

[figure not shown]
To investigate the potential impact of missing data on the primary efficacy analysis if nonignorable censoring is differential, a sensitivity analysis similar to sensitivity analyses based on pattern-mixture models described by the NRC (NRC 2012) will be employed.

Primary efficacy outcome events in subjects with missing rivaroxaban/aspirin follow-up data will be generated in a three-step process by

- (1) defining a cohort (pattern) of subjects from whom information about the unobserved event process is borrowed and estimation of individual hazards from an imputation model

- (2) simulation of primary outcome events using individualized hazard estimates at the censoring date to create multiple data sets with imputed data; fitting of the primary analysis model to the imputed data sets; combining the analysis results to generate statistical inference
- (3) assessment of the robustness by repetition of step 2 after inflation of the individual hazard estimates in the rivaroxaban treatment groups and determination of the “tipping point”.

The subdivision of the ITT set as described in the following steps is illustrated by [Figure 10-1](#).

**Figure 10-1 Subdivision of ITT set for estimation of individual hazards for imputation**

**Step 1:**

According to the study protocol all subjects are to be followed until the end of the rivaroxaban/aspirin follow-up / end of the study and data on the primary efficacy outcomes are collected irrespective of whether or not a subject is on or off anti-thrombotic treatment. The cohort of subjects who prematurely discontinue any anti-thrombotic study treatment (i.e. either study

rivaroxaban bid and/or study aspirin treatment) will be used for imputation of unobserved follow-up time.

More specifically, for subjects who prematurely discontinued any anti-thrombotic study treatment, a Weibull survival model will be fitted to estimate the individual hazard of a primary outcome event at the last contact date of the rivaroxaban/aspirin portion of the trial. The model will be adjusted for treatment groups (rivaroxaban 2.5 mg bid + aspirin 100 mg od, rivaroxaban 5 mg bid + aspirin placebo od, rivaroxaban placebo + aspirin 100 mg od), stratification factor (not randomized to a proton pump inhibitor; pantoprazole 40 mg od; pantoprazole placebo) and the following baseline covariates:

- CAD and PAD, CAD only, PAD only
- Age (<65, 65 years or older)
- Region (North America, Western Europe, Eastern Europe, Asia Pacific and other, and South America)
- History of a prior heart failure
- History of prior stroke
- History of prior MI

The imputation model will also include a covariate indicating the occurrence of a major bleeding event (post-randomization event), if the bleeding occurred (start date) during the 90 days preceding the unrefuted primary efficacy outcome event or the censoring date relevant for primary analysis:

If the individual hazard for a subject cannot be estimated from the above model due to missing covariates the hazard estimate from a crude model – adjusted for treatment groups and stratification factor only – will be used for this subject (see Section 10.4.4).

### Step 2:

For subjects with missing rivaroxaban/aspirin follow-up time who did not experience an unrefuted primary outcome event and were alive at censoring, random variables reflecting a subject's individualized hazard (from step 1) will be simulated using the conditional time to event distribution after the last available rivaroxaban/aspirin follow-up (see Section 10.4.5). If this randomly generated variable has a value less than the elapsed time between the last available rivaroxaban/aspirin follow-up date (exclusive) and the "global rivaroxaban/aspirin outcomes cut-off date" (inclusive), the subject will be treated as having an primary efficacy event occurring at the date of last available rivaroxaban/aspirin follow-up plus the value from the random variable. Otherwise, the subject is re-adjusted to be censored at the "global rivaroxaban/aspirin outcomes cut-off date". Events and time at risk is imputed assuming that no death due to non-CV causes occurs.

Imputed events and event-free time at risk will be added to the observed events and times under risk in the study and the primary efficacy analysis will be repeated: The Cox proportional-hazards models from primary efficacy analysis will be fitted to the imputed data sets. This imputation and

---

 Experience shows that exponential distribution adequately models the survival time. In case of deviating data this approach can easily be extended to Weibull distribution by estimating the scale parameter  $\sigma$ .

analysis of primary outcome events will be repeated 1,000 times. Inferences for combined parameters will be done using multiple imputation rules that reflect imputation uncertainty (see Section 10.4.6).

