### 10.4.4 Parameter estimation

For subjects who prematurely discontinued any anti-thrombotic study treatment, a Weibull survival model will be fitted to estimate the hazard of a primary outcome event at the last contact date in the rivaroxaban/aspirin portion of the trial:

```
PROC LIFEREG DATA = <dataset> OUTEST=<dataset1>;
  MODEL ttevalue*ttecnsr(1) = trtgrp stratum <covariates> /
    DISTRIBUTION = weibull INTERCEPT=8 INITIAL=0.2;
  OUTPUT OUT=<dataset2> CDF=cdf XBETA=xbeta;
RUN;
/*
where
dataset = name of sub-dataset including all ITT subjects who prematurely
discontinued any anti-thrombotic study treatment
dataset1 = SAS data set containing the parameter estimates
dataset2 = SAS data set containing statistics (CDF and x'β) calculated after
fitting the model
ttevalue = time to first occurrence of primary efficacy outcome event
ttecnsr = censoring index (1 = right-censored, 0 = event)
trtgrp = variable coding randomized antithrombotic treatment group
        (0 = control group, 1 = rivaroxaban 2.5 mg + aspirin 100 mg)
stratum = variable for PPI stratification factor (three levels)
*/
```

The SAS LIFEREG procedure will be used to model the natural logarithm  $w = \log(t)$  of the survival time. The survival function used by SAS has the form

$$S(w) = \exp\left(-\exp\left(\frac{w-\mu}{\sigma}\right)\right),$$

where  $\mu$  is the location parameter and  $\sigma$  the scale parameter.

Re-parameterization by  $\lambda = \exp(\mu)$  and  $\beta = 1/\sigma$  results in the survival function  $S_1$  with

$$S(w) = S_1(t) = \exp\left(-\left(\frac{t}{\lambda}\right)^\beta\right).$$

The estimated hazard at the last contact date in the rivaroxaban/aspirin portion of the trial will be obtained from the fitted Weibull model, adjusted for treatment and baseline covariates for each subject.

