#### 10.4.5 Generation of random variables

Let the survival time  $T$  be Weibull distributed, with survival function  $S_1$ .

The conditional distribution function of  $T$  after the censoring date  $CD$  (given that no event was observed before) is given for  $s \geq 0$  by

$$\begin{aligned} G(s) := P(T \leq s + CD | T > CD) &= 1 - P(T > s + CD | T > CD) = 1 - \frac{P(T > s + CD)}{P(T > CD)} \\ &= 1 - \frac{S_1(s + CD)}{S_1(CD)}. \end{aligned}$$

With scale parameter  $\lambda$  and shape parameter  $\beta$  from the underlying Weibull distribution we have

$$G(s) = 1 - \frac{\exp\left(-\left(\frac{s + CD}{\lambda}\right)^\beta\right)}{\exp\left(-\left(\frac{CD}{\lambda}\right)^\beta\right)},$$

hence

$$G^{-1}(s) = \lambda \left( \left( \frac{CD}{\lambda} \right)^\beta - \log(1 - s) \right)^{1/\beta} - CD.$$

If  $s$  is generated as a random variable with uniform distribution between 0 and 1, a random variable with distribution function  $G$  can be generated using the inverse transformation technique from

$$\lambda \left( (CD/\lambda)^\beta - \log(1 - \text{rand}('uniform')) \right)^{1/\beta} - CD.$$

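### The missing-data tipping-point analysis reuses one fixed set of Weibull estimates in all 1,000 imputations, so its pooled intervals are slightly too narrow and its tipping factors slightly too high.

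*SAP*

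**What the plan says.** The procedure is fixed in SAP Sections 10.4.3 to 10.4.6.

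- **Fit (Step 1 and Section 10.4.4).** The donors are those who came off either randomized antithrombotic drug early, and the model is Weibull. Step 1 reads: "survival model will be fitted to estimate the individual hazard of a primary outcome event at the last contact date". The code is a single call, "PROC LIFEREG DATA = <dataset> OUTEST=<dataset1>", and its output is described as a "SAS data set containing the parameter estimates". No covariance output, bootstrap, parameter draw or refit per imputation is specified. Section 10.4.4 adds: "The estimated hazard at the last contact date in the rivaroxaban/aspirin portion of the trial will be obtained from the fitted Weibull model".
- **Draw (Step 2 and Section 10.4.5).** A residual event time "can be generated using the inverse transformation technique from" a formula in which the scale and shape are constants. The only random element is one uniform variate per subject.
- **Repetition (Step 2).** The imputation and "analysis of primary outcome events will be repeated 1,000 times". The Step 1 fit lies outside that loop. Section 10.4.6 runs the Cox model by imputation number and pools with PROC MIANALYZE.
- **Tipping point (Step 3).** This is the "assessment of the robustness by repetition of step 2 after inflation of the individual hazard estimates in the rivaroxaban treatment groups". F and G are the factors at which the upper 95% limit of each hazard ratio crosses 1. The grid runs in steps of 10% to 200%, 50% to 500% and 100% to 1000%.

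Step 2 describes the pooling in these words: "Inferences for combined parameters will be done using multiple imputation rules that reflect imputation uncertainty".

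**The concern.** Rubin's rules give a valid total variance only if the between-imputation spread covers everything uncertain about the imputed values. There are two sources here: the randomness of an event time given its hazard, and the uncertainty of the hazard itself, which is estimated from a limited donor cohort. The stated algorithm varies only the first. This is improper multiple imputation, and raising the number of imputations to 1,000 reduces Monte Carlo error without supplying the missing component.

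The stake is the reading of F and G. If the upper limit is too low, it reaches 1 at too large an inflation factor, and the result looks more robust to informative loss to follow-up than it is. For a given amount of missing follow-up the shortfall grows with the inflation factor, because the error in the base hazard is scaled along with the hazard.

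**Working it through.** The SAP gives no missing fraction, pooled variance or tipping factor, so there is no figure of its own to reproduce. The sampler itself is correct: simulating from the Section 10.4.5 formula returns the stated conditional Weibull distribution (0.06244 against 0.06244 exact).

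**Inputs from the SAP**
- Events at the first interim look: about 1,100 (Section 4.4). With the planned split 826 : 687 : 687 this is 1,100 × 826/2,200 = 413 control and 1,100 × 687/2,200 ≈ 344 per rivaroxaban arm. A hazard ratio of 0.80 gives 0.80 × 413 ≈ 330.
- Donor cohort: 27,400 subjects at 2.9% per year (Section 7) reach 1,100 events after 1,100/(27,400 × 0.029) ≈ 1.38 years and 1,650 after 2.08 years. Discontinuation of 6%, 4.5%, then 3% per half-year gives 12.3% and 15.9% off treatment. That is roughly 40 to 80 donor events per arm, so the standard error of the log hazard is about 1/√80 = 0.11 to 1/√40 = 0.16.

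**Assumptions not in the SAP**
- Missing follow-up 0.5% to 3% of subject-years; donor hazard 4% per year; standard error *s* of the log hazard 0.10 to 0.20.
- 18,000 subject-years per arm. Since 413/18,000 is 2.3% per year against the SAP's 3.3% for control, 12,500 (413/0.033) was also tried.

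**Formulae** (events-based approximation, equal time at risk per arm). *d* is observed events, *M* missing subject-years, *E* imputed events: 0.04 × *M* in control and *F* × 0.04 × *M* in the rivaroxaban arm.
- log HR = ln[(d₁ + E₁)/(d₀ + E₀)]
- Variance as planned = Σ [1/(d + E) + E/(d + E)²]
- Omitted term = Σ [E·s/(d + E)]²
- The tipping multiple *F* solves log HR + 1.96·SE = 0.

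**Worked case:** 413 and 330 events, 18,000 subject-years, 1% missing, *s* = 0.15.
- M = 180 and E₀ = 7.2. At F = 4.683, E₁ = 33.7.
- log HR = ln(363.7/420.2) = −0.1444.
- Planned variance = 0.002750 + 0.002380 + 0.000255 + 0.000041 = 0.005426. SE = 0.0737 and 1.96·SE = 0.1444, so this is the planned tipping point.
- Omitted term = 0.000193 + 0.000007 = 0.000200. The SE becomes 0.0750, the upper limit there is about 1.003, and the tipping multiple falls to 4.555.
- Inflation of 368% and of 356% are both first reached at the 400% step, so the reported factor is unchanged.

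**Across the range** (a multiple of 2.0 is read as 100% inflation):

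| Subject-years per arm | Rivaroxaban events | Missing | s | Multiple: planned → redrawn | Too high by | Grid step |
|---|---|---|---|---|---|---|
| 12,500 | 344 | 0.5% | 0.10 | 6.46 → 6.42 | 0.6% | 600% → 600% |
| 18,000 | 330 | 0.5% | 0.20 | 8.49 → 8.14 | 4.4% | 800% → 800% |
| 18,000 | 344 | 2% | 0.15 | 1.84 → 1.79 | 2.6% | 90% → 80% |
| 18,000 | 330 | 2% | 0.20 | 2.78 → 2.62 | 6.0% | 180% → 170% |
| 12,500 | 330 | 3% | 0.20 | 2.70 → 2.55 | 6.1% | 180% → 160% |
| 18,000 | 330 | 3% | 0.20 | 2.14 → 2.00 | 7.2% | 120% → 100% |

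**Simulation check.** 6,000 replicates with 9,134 subjects per arm, control rate 3.3% per year, hazard ratio 0.80 and 12.3% donors; all but the hazard ratio follow from Section 7. With 5% missing:

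| Multiplier | True SD | SE as planned (coverage) | SE with omitted term (coverage) |
|---|---|---|---|
| 1 | 0.0769 | 0.0763 (94.6%) | 0.0770 (94.8%) |
| 3 | 0.0787 | 0.0758 (93.9%) | 0.0791 (95.0%) |
| 6 | 0.0823 | 0.0747 (92.4%) | 0.0835 (95.2%) |

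With 1% missing the two SEs differ by under 0.1% at multiplier 1 and by 1.5% at multiplier 10. Without inflation the upper limit of the hazard ratio moves by at most about 0.0014 up to 5% missing.

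**The case against.** There is a fair case for the plan as written, and most of it is correct.

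- **The quoted sentence describes the combining rules.** MIANALYZE does add between-imputation variance for the event times, and the SAP nowhere promises parameter draws. This stands: the property is partly delivered, not absent.
- **The grid absorbs most of the error.** Above 200% the steps are 50% and then 100%. A reader counting in tens of percentage points might infer a shift of three or four steps from 8.49 against 8.14, but both are reported as 800%. This stands.
- **Other parts of the design bound the problem.** Section 4.2 expects very few subjects with incomplete follow-up. Step 3 multiplies rivaroxaban hazards far beyond their sampling error, and the analysis is repeated with a model fitted to all randomized subjects. With 330 rather than about 40 events in an arm, the standard error of its log hazard is 1/√330 = 0.055 rather than 0.16. These points limit the size, but none puts the omitted term into the interval.
- **Nothing is decided by F or G.** They have no pass mark and belong to exploratory analyses. This stands, and is why the point is minor.

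A reader might also infer that the error is worst where the tipping factor is largest. That holds only for a fixed amount of missing data. Across scenarios, more missing follow-up lowers the tipping factor and raises the relative error.

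**Conclusion.** The point holds as a minor flaw in one direction. As written, the pooled intervals leave out estimation error in the borrowed hazards, so F and G are biased upward. Under the stated assumptions the tipping multiple is about 0.6% to 7% too high, usually zero or one step on the SAP's grid and at most two.

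The size depends on the missing fraction, the donor hazard, its standard error and the observed hazard ratio, none of which the SAP gives. The approximation also ignores covariates and holds the Weibull shape fixed; estimating both would add somewhat to the omitted error. If missing follow-up reached 10%, a separate run found a two-step move (170% to 150%, at an assumed hazard ratio of 0.748).

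The documents do not support the stronger inference that the missing-data analysis is invalid or that the efficacy conclusion is in doubt. The primary log-rank test, the Cox estimate and the gatekeeping procedure do not use the imputation model.

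**What to change.** In Sections 10.4.3 to 10.4.5, make the Weibull parameters random across imputations, in one of two ways:

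1. Add COVOUT to the OUTEST= request in PROC LIFEREG. For each imputation, draw the full parameter vector from a multivariate normal with the estimated mean and covariance matrix.
2. For each imputation, refit the Weibull model on a bootstrap sample of the donor cohort.

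Then compute the individual hazards, apply the inflation factor and draw event times as now. Do the same for the repeat analysis fitted to all randomized subjects, and for the crude model used when covariates are missing. PROC PHREG and PROC MIANALYZE stay as they are.

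The cost is a few lines of SAS, some run time and slightly wider intervals. If the sponsor keeps the present algorithm, the appendix should say that the pooled intervals treat the imputation hazards as known.
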